Our secondary aim is to determine whether the intervention affects 1) the frequency of positive-urine tests for opioids and 2) the frequency and proportion of subjects self-reporting opioid use. (We recognize that, due to constraints on in-person follow-up imposed by the COVID-19 pandemic, individuals who are most likely to get urine tests are those who are in treatment and those who might subsequently present to the emergency department (ED) for opioid-related complaints.) Our hypothesis is that our intervention will decrease both. As in the previous aim, data will be collected remotely/electronically from self-report and EPIC. If the sources of information were to conflict, then what is entered in EPIC will take precedence.

Data from our entire cohort will be compared in aggregate with patients who were started on BUP in the ED over the same time period and with historic controls who received only printed resources addressing OUD as reported in [name] et al.¹¹

2. Probable Duration of Project: State the expected duration of the project, including all follow-up and data analysis activities.

The probable duration of the project is 2 years (from 09/2019-09/2021). There is potential for extension after this time, depending on availability of funding.

3. Background: Describe the background information that led to the plan for this project. Provide references to support the expectation of obtaining useful scientific data.

Importance of problem.

The epidemic of opioid use disorder (OUD) prompted a presidential declaration of a public health emergency in October, 2017, and it was extended in January, 2018.² In 2016, an unprecedented 63,632 deaths in the United States (US) were attributed to drug overdose; 2/3 of these involved opioids.³ The deaths due to drug overdose in 2016⁴ exceeded the number of traffic fatalities during the peak year of 1972,⁵ the number of HIV deaths at their peak in 1995, the final year before the introduction of triple antiviral therapy,⁶ and the peak year for gun violence in the US, which was 1993.^{7,8} Nonfatal opioid overdoses are highly associated with ongoing OUD and recurrent overdoses. One study reviewing emergency medical service (EMS) records of

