There has been extensive prior literature comparing treatment modalities for patients with OUD. In these studies, the arms are rigidly controlled to assess efficacy of the treatments. While BUP is currently considered the most effective treatment, many patients decline to start it after an overdose, and a substantial proportion of those who do start it do not achieve remission of their OUD. Less than half of patients who start it remain engaged in treatment at the time of follow up, though the proportion still engaged in treatment with BUP is roughly double that of the patients who are treated only with BNI or community referral. Investigators both here and in large, multicenter trials have found that outcomes of BUP therapy were not substantially improved by the addition of adjunctive counselling or cognitive behavioral therapy.³¹⁻³³ Adjunctive counselling was not shown to improve outcomes of patients on BUP in any of these studies. It should be noted, however, that the counselling was scripted and manual-driven to ensure consistency. Further, in one of the reports,³³ all patients were tapered off the BUP during the study with a predictable high relapse rate. Our study will demonstrate whether a more patient-centered approach, combining motivation to treatment while providing connections to continuous, community-based medical and psychosocial support, can improve outcomes compared with historical and concurrent controls. Positive findings in this study will further broaden the potential scope of mobile integrated health care, an emerging aspect of EMS. It may also reveal a synergistic effect of the traditionally community-oriented recovery model using peer coaches with the best medical management. If we find that our cohort of patients managed through this collaborative approach has improved outcomes, studies in the field will become even more complex, as it will be clear that interventions probably cannot be compared in isolation, but will be carried out with customized and adaptable supportive care.

Innovation.

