Consent may be obtained at the ED, during community outreach events, electronically in a Yale School of Medicine version of REDCap®, or remotely (e.g., via email or picture), in accordance with University guidelines issued on 05/21/2020 from the Yale Center for Clinical Investigation. After consent and study initiation, either at the hospital or at some other time, the RCP team will perform a BNI—whose goal is to employ motivational techniques to help those with substance abuse consider their reasons for wanting to address dependency. Electronically, the RCP team will perform psychosocial and medical evaluations. (Please see the document, *Survey Tool and Handbook*, for details. It is included in our submission materials.) The RCP team will enter all data into a secured, encrypted database, REDCap®. To obtain consent or approximately 30 days after consent, the RCP team will schedule an electronic/remote (including by phone) Meeting 1 with participants. During this time, by remote interventions, the RCP team will collect and enter data into REDCap® based on discussions with and evaluations of participants. During an electronic/remote (including by phone) Meeting 2, which should occur no more than 180 days after consent, the RCP team will also collect and enter data into REDCap® based on discussions with and evaluations of participants. The study team will also enter data from participants' medical records at all time intervals. It is important to underscore that, due to the coronavirus pandemic, electronic and remote (including by phone) modalities will be utilized to the greatest extent possible.

Data from the entire cohort will be compared in aggregate with patients who were started on BUP in the ED over the same time period and with historic controls.¹¹

Figure 1. Screening + Enrollment

Genetic Testing N/A

A. Describe

- i. the types of future research to be conducted using the materials, specifying if immortalization of cell lines, whole exome or genome sequencing, genome wide association studies, or animal studies are planned *Write here*
 - ii. the plan for the collection of material or the conditions under which material will be received *Write here*
 - iii. the types of information about the donor/individual contributors that will be entered into a database *Write here*
 - iv. the methods to uphold confidentiality *Write here*

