3. Screen positive for OUD using mini international neuropsychiatric interview (MINI) (if applicable)	+	-
4. At least 1 opioid overdose requiring resuscitation by naloxone	+	-
5. Have a non-opioid overdose explanation for decreased level of consciousness, miosis, or decreased respiratory rate (if applicable)	-	+
6. Positive for OUD using a health questionnaire containing questions about prescription opioid and heroin use	+	-
7. Not in a critically ill state at the time of consent (e.g., not actively suicidal, psychotic, septic, and/or experiencing cardiac arrest)	+	-
8. 3.,4., & 6. (in this column) must have occurred within ≤ 7 days (inclusive) from date of consent if the prospective participant were immediately discharged from the emergency department (ED), floor, or other health care facility; consent may be obtained at any of these locations	+	-
9. Homicidal	-	+
10. Able to consent to program/study participation	+	-
11. Permanent residence is a long-term care/skilled nursing facility	-	+
12. Simultaneously enrolled in another study whose principal investigator (PI) or co-PI is a faculty member in the Department of Emergency Medicine	-	+
13. Prescribed opioids for acute pain, chronic pain, or palliative care without OUD	-	+
14. Stably enrolled in opioid agonist treatment or other medication-assisted therapy for OUD at the time of consent	-	+
15. In police custody or incarcerated (at the time of consent to participate or any known time after). (Parolees & those on probation may be eligible, but are NOT the target population and may be enrolled only incidentally .)	-	+
16. Refused buprenorphine/naloxone (BUP), if offered	+	-
17. Has a mailing address or P.O. box	+	-
18. Able to answer questions electronically/remotely (including by phone)	+	-

8. How will **eligibility** be determined, and by whom? *Write here*

In general, eligibility will be determined by the RCP team. ED and study staff may assist occasionally.

9. **Risks:** Describe the reasonably foreseeable risks, including risks to subject privacy, discomforts, or inconveniences associated with subjects participating in the research.

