
- d. For multi-site studies for which the Yale PI serves as the lead investigator: N/A
 - i. How will adverse events and unanticipated problems involving risks to subjects or others be reported, reviewed and managed? N/A
 - ii. What provisions are in place for management of interim results? N/A
 - iii. What will the multi-site process be for protocol modifications? N/A

12. **Statistical Considerations:** Describe the statistical analyses that support the study design.

Study design

Primary outcomes

The primary outcomes will be 1) percentage of individuals with repeat opioid overdose events requiring naloxone resuscitation, identified using YNHH's electronic medical record system (EPIC), and 2) percentage of individuals engaged in any treatment for OUD or who are in remission. Data will be recorded at baseline and at 30 and 180 days after consent to participate in the research.

Secondary outcomes

The secondary outcomes will be 1) frequency and percentage of individuals with positive opioid tests (urine) recorded in their hospital charts or during medication program monitoring, and 2) frequency and percentage of subjects with self-reported opioid use. Data will be recorded at baseline and at 30 and 180 days after consent to participate in the research.

Statistical analyses

We will document demographics (sex, race/ethnicity, age, education, employment status, etc.) and clinical characteristics (e.g., heroin use, non-opioid use in the past 6 months, lifetime treatment for addiction etc.) among all cohorts. χ^2 tests (2 df) will be employed to detect statistically significant differences.

Group	X	No X	Total
PRIDE + CCAR intervention			
BUP-initiated in ED after OD			
Historical control(s)			
Total			

For primary outcomes, "X" is % of repeated overdose events or % of treatment engagement. For secondary outcomes, "X" is frequency or % positive testing for opioid tests or % (self-reported) opioid abuse.

Sample size determination

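### The only outcome test, an unadjusted three-cohort chi-square, does not isolate the RCP intervention and leaves case mix in the comparison

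*Combined protocol and SAP*

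**What the plan says.** All references are to the combined protocol and SAP.

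- **Cohorts.** Eligibility item 16 (Section I, item 7) requires RCP participants to have "Refused buprenorphine/naloxone (BUP), if offered". The Research Plan (item 4) adds the concurrent comparator: "Data from the entire cohort will be compared in aggregate with patients who were started on BUP in the ED". The aims describe the third cohort as "historic controls who received only printed resources addressing OUD as reported in" a cited publication.
- **Analysis.** Under Statistical analyses (item 12), the plan states "We will document demographics (sex, race/ethnicity, age, education, employment status, etc.) and clinical characteristics" for all cohorts. The next sentence says chi-square "tests (2 df) will be employed to detect statistically significant differences". The table below it has one row per cohort and columns X, No X and Total, where X is each primary or secondary outcome in turn.
- **Question.** The Background says the study will show whether the approach "can improve outcomes compared with historical and concurrent controls". The aims and the Research Plan hypothesise, specifically for the RCP team, fewer overdoses and more remission.

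For this study, the document contains no pairwise contrast, regression, stratification, matching, weighting or multiplicity rule, and no caveat about confounding between cohorts. The one multivariable analysis it mentions belongs to a cited background study.

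**The concern.** There are two problems.

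**The test does not match the question.** A 2-df test across three groups can be significant only because the two comparators differ from each other. The Background gives reason to expect that they do, since it puts engagement on BUP at roughly twice that with brief interview or community referral. A significant result would then say little about RCP.

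**The cohorts are not alike by construction.** One refused BUP or was not offered it, one accepted it, and one comes from an earlier publication. A crude difference, or the lack of one, mixes any intervention effect with case mix. The variables that could address part of this are to be documented but enter no outcome comparison.

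At stake is whether the study can say anything specific about RCP, which is what its hypothesis and Background promise.

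**Working it through.** **1. The plan's own figure.** Three cohorts by two outcome categories give (3 − 1)(2 − 1) = 2 df, as stated. The test is therefore the three-group omnibus test.

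**2. Inputs for the omnibus check (treatment engagement).**
- From the Background: fewer than half of those who start BUP stay engaged, about double the proportion with brief interview or referral.
- Assumed: BUP engagement b of 40%, 45% or 49%, and historical controls at b/2. The historical controls received printed resources, so giving them the referral rate is itself an assumption.
- Cohort sizes: the plan gives about 100 people and no split. I used 33/33/34 (100 as the total) and 100 per group (100 as the RCP cohort alone).

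**3. Formula.** With p̄ the pooled rate, λ = Σ nᵢ(pᵢ − p̄)² / [p̄(1 − p̄)], and power is the upper tail of a noncentral chi-square with 2 df beyond the 5% critical value.

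Worked at 33/33/34 and b = 40%, in the order RCP, BUP, historical:
- RCP no better than historical (20/40/20%): p̄ = (6.6 + 13.2 + 6.8)/100 = 0.266. λ = (33×0.066² + 33×0.134² + 34×0.066²)/(0.266×0.734) = 4.53, so power is 46.3%.
- RCP equal to BUP (40/40/20%): p̄ = (13.2 + 13.2 + 6.8)/100 = 0.332. λ = (66×0.068² + 34×0.132²)/(0.332×0.668) = 4.05, so power is 42.0%.

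Share of studies with a significant 2-df test, by simulation (100,000 replicates; formula value in brackets):

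| Sizes | b | RCP = historical | RCP = BUP |
|---|---|---|---|
| 33/33/34 | 40% | 46.1% (46.3) | 42.9% (42.0) |
| 33/33/34 | 45% | 52.6% (53.2) | 50.0% (49.1) |
| 33/33/34 | 49% | 58.5% (58.7) | 55.7% (55.2) |
| 100 each | 40% | 91.4% (92.1) | 90.5% (88.3) |
| 100 each | 45% | 95.4% (95.7) | 94.9% (93.5) |
| 100 each | 49% | 97.3% (97.6) | 97.2% (96.3) |

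The two columns are nearly the same. Significance does not separate an intervention with no gain over historical controls from one that does as well as BUP.

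**4. Case mix.** The documents give no inputs, so everything here is assumed: no group effect, and one binary prognostic factor with outcome rate r0 without it and r1 with it. The crude rate is r0 + prevalence × (r1 − r0).

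| r0, r1 | Prevalence in the three cohorts | Crude rates | Rejects, 100 each | Rejects, 33 each |
|---|---|---|---|---|
| 30%, 60% | 40/50/60% | 42/45/48% | 11% | 7% |
| 30%, 60% | 30/50/70% | 39/45/51% | 31% | 13% |
| 5%, 15% | 40/50/60% | 9/10/11% | 7% | 5% |
| 5%, 15% | 30/50/70% | 8/10/12% | 12% | 6% |

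With equal rates of 45%, the same test rejects about 5% at both sizes. For a rarer outcome such as repeat overdose, rejection can therefore stay near nominal.

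**5. Power of a separate RCP versus historical contrast.** Use 33 versus 34 people and the rates in step 2, with RCP equal to BUP. Power = Φ[(d − 1.96·se₀)/se₁], where d is the difference, se₀ the pooled and se₁ the unpooled standard error.
- b = 40%: Φ[(0.200 − 1.96×0.1118)/0.1094] = 43%. Exact binomial enumeration gives 44%.
- b = 49%: Φ[(0.245 − 1.96×0.1177)/0.1141] = 55%. Exact enumeration also gives 55%.
- At two-sided 2.5% (Bonferroni for two contrasts), the range is 32–44%.
- At 100 per group and 5%, the range is 88–95%.

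**The case against.** **The chi-square sentence follows the baseline sentence, so it may concern baseline.** It may cover baseline as well. But the table beneath defines X as the outcomes, and baseline testing is not adjustment. If the sentence covered baseline only, no outcome test would be specified at all.

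**The table shows each cohort's rate, and pairwise tests after a significant three-group test are ordinary practice.** That is fair, and it is why the fix is cheap. But the plan does not state such tests, nor an effect measure, interval or multiplicity rule for them.

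**Adjustment cannot rescue the design.** This stands. Concurrent patients accepted BUP; RCP participants refused it or were not offered it. There is almost no overlap on that factor, so listing it as a covariate would not help. Adjustment can deal only with other measured differences.

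**Stronger readings that a reader might infer.**
- *The crude result is biased in a known direction or by a known amount.* The case-mix figures rest wholly on assumptions, and for rarer outcomes they are often near 5%.
- *Eligibility item 14, which excludes those "Stably enrolled in opioid agonist treatment or other medication-assisted therapy for OUD at the time of consent", is a further cohort difference.* Patients newly started on BUP in the ED were presumably not stably enrolled either, and no eligibility rules are given for either comparator. Item 14 shows no contrast.
- *Comparator follow-up is misaligned.* The plan says "Data will be recorded at baseline and at 30 and 180 days after consent to participate in the research" and does not say when counting starts for the comparators. That is a separate gap, with no demonstrated effect here.

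**Conclusion.** The concern holds for the analysis as written. The only stated outcome test cannot answer the RCP-specific question. Under the Background's own expectation for engagement, it is significant about as often when RCP is no better than historical controls (about 46–59% at 33/33/34; 91–97% at 100 per group) as when RCP matches BUP (43–56%; 90–97%). This rests on BUP engagement of 40–49%, historical controls at half that, and the two readings of cohort size. It concerns engagement, not repeat overdose.

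That the crude comparison is open to case-mix differences follows from how the cohorts are formed. How large the distortion is, and which way it runs, cannot be derived from the documents.

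A reader might also infer that an adjusted model would let the study establish an effect of RCP. The documents do not support that, because acceptance or refusal of BUP largely defines who is in which cohort. The change is worth making before analysis and does not require a new design.

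**What to change.** 1. Keep the crude three-row table as description. Pre-specify RCP versus concurrent BUP and RCP versus historical controls as two separate contrasts, each with a risk difference and 95% confidence interval. State a multiplicity rule, for example Holm, if both are tested.
2. If individual data on concurrent BUP patients are usable, add a supportive covariate-adjusted RCP versus BUP risk difference for treatment engagement or remission. Use a short named set from the variables already listed in item 12, such as age, sex, heroin use, non-opioid use in the past 6 months and lifetime addiction treatment.
3. Report repeat overdose unadjusted and descriptively if events are few. At an assumed 10% rate, two cohorts of 100 give 20 events, or 20/3 = 6.7 per parameter for group plus two covariates. Two cohorts of 33 give 6.6 events, or 2.2 per parameter.
4. Label the historical contrast descriptive if only published aggregates exist.
5. State that acceptance versus refusal of BUP cannot be adjusted away, and soften the Background's promise of a demonstration to one of association.

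**Cost.** Wording and some extra analysis work. Power per contrast is lower: about 44–55% for RCP versus historical at 33–34 per group before multiplicity, under the assumptions above. Intervals are wide: the half-width is 1.96×0.1094, about 21 points, at 33/34 and b = 40%. Individual comparator data may need privacy or ethics review, because the plan describes an aggregate comparison and the rationale for the HIPAA waiver concerns finding prospective participants.

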Our principal aim is to determine whether a novel biopsychosocial intervention following opioid overdose (OD) affects 1) the frequency of secondary opioid OD events and 2) the proportion of individuals who remain engaged in treatment for opioid use disorder (OUD) or are in remission at 30 days and at 180 days post consent. We define remission as engagement in daily medication-assisted therapy (MAT)—typically buprenorphine/naloxone (BUP) or methadone—and/or a recovery capital score of ≥ 27.5 .¹ Our intervention will connect individuals with important community resources that hopefully will facilitate progress toward long-term recovery. Specifically, we will link individuals with moderate-severe OUD, who have experienced at least 1 opioid OD requiring naloxone resuscitation but refused BUP treatment, if offered, with 1) treatment with BUP, 2) methadone maintenance, intensive outpatient, or residential treatments, or 3) education materials from the Connecticut Community for Addiction Recovery (CCAR). Enrolled participants may switch from 1)-3) throughout. To carry out the intervention, an addiction recovery coach from CCAR and a health educator (research) paramedic will form a team (RCP team) and perform remote (including over-the-phone) and/or electronic follow-up visits after a participant has experienced at least 1 opioid OD requiring naloxone resuscitation. Our hypothesis is that the intervention, by the RCP team, connecting participants to community resources will decrease subsequent OD events and increase the likelihood of remission. To evaluate this hypothesis, data will be collected from self-report and from EPIC, Yale New Haven Hospital's (YNHH) medical record system. If the sources of information appear to conflict, then what is entered in EPIC will take precedence.

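### The three-cohort 2-df chi-square does not test the stated hypothesis about the RCP intervention; section 12 needs a named RCP contrast and a decision rule

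*Combined protocol and SAP*

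**What the plan says.** Section I, item 12 (Statistical Considerations) lists two primary outcomes: the percentage with a repeat opioid overdose needing naloxone, and the percentage engaged in treatment or in remission. On timing it says: "Data will be recorded at baseline and at 30 and 180 days after consent".

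Under Statistical analyses, chi-square "tests (2 df) will be employed to detect statistically significant differences". A table follows with three rows (RCP intervention, BUP started in the ED, historical controls) and two columns (X, no X). Its note says that for the primary outcomes X "is % of repeated overdose events or % of treatment engagement". Sample size determination adds about 100 individuals, 80% power and a 5% significance level.

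The hypothesis, in the opening aims and again in item 4 (Research Plan), concerns RCP alone and has a direction: "connecting participants to community resources will decrease subsequent OD events and increase the likelihood of remission".

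The comparators are named outside item 12. Item 4 says "Data from the entire cohort will be compared in aggregate with patients who were started on BUP in the ED" over the same period and with historic controls. The aims describe the latter as "historic controls who received only printed resources addressing OUD". The Background asks whether the approach "can improve outcomes compared with historical and concurrent controls".

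No section says which RCP comparison is primary, how a significant 2-df result is followed up, which of days 30 and 180 is primary, or what result would count as success.

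**The concern.** The hypothesis is a directional statement about one cohort. The 2-df chi-square asks whether three proportions are all equal, and its statistic has no direction. The protocol itself expects two of the three rows to differ: on engagement, "the proportion still engaged in treatment with BUP is roughly double that of the patients who are treated only with BNI or community referral". A small p-value could therefore arise mainly because BUP does better than the historical control, and then be reported as support for RCP.

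Beating printed resources and beating ED-started BUP are also different claims. As written, the investigators would choose between them after seeing the three proportions.

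**Working it through.** **The plan's own figure.** The only number available to reproduce is about 100 individuals. Treating the quoted effect sizes as Cohen's w (an assumption), a 2-df test at 5% with 80% power needs a noncentrality of 9.635, so N = 9.635/w². This gives 241 at w = 0.2, 61 at w = 0.4 and 39 at w = 0.5. N = 100 corresponds to w = √(9.635/100) = 0.31, which lies inside the quoted 0.2-0.4 but is not stated. The figure is neither confirmed nor refuted, and the point below does not depend on it.

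**What rejection means.** The null is p(RCP) = p(BUP) = p(control), which is the same as RCP = BUP and RCP = control. If it is false, RCP differs from at least one comparator. Which one, and in which direction, is left open.

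**How often the test rejects when RCP equals control.** All rates and cohort sizes are assumptions. The Background gives only under half for BUP engagement and about a 2:1 ratio, and no per-cohort sizes are stated. With p̄ the weighted mean proportion:

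λ = Σ nᵢ(pᵢ − p̄)² / [p̄(1 − p̄)]; power = P(noncentral χ², 2 df, λ > 5.99)

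Example, 22.5/45/22.5% at 100 each: p̄ = 0.30; λ = 100 × (2 × 0.075² + 0.15²)/0.21 = 3.375/0.21 = 16.07; power 0.957.

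| RCP/BUP/control | 100 each | 33 each |
|---|---|---|
| Engagement 24/48/24% | 0.972 | 0.570 |
| Engagement 22.5/45/22.5% | 0.957 | 0.529 |
| Engagement 20/40/20% | 0.921 | 0.460 |
| Engagement 15/30/15% | 0.788 | 0.330 |
| Composite 35/45/35% | 0.304 | 0.127 |
| Overdose 20/10/20% | 0.487 | 0.186 |
| Overdose 15/7.5/15% | 0.362 | 0.145 |
| Overdose 10/5/10% | 0.243 | 0.108 |

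Simulated overdose values are close at 100 each (0.504, 0.367, 0.235) and slightly lower at 33 each (0.183, 0.136, 0.082).

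**One concrete table.** RCP 30/100, BUP 40/100, control 20/100. Expected count 30 per row, so χ² = (0 + 10² + 10²)/(30 × 0.7) = 200/21 = 9.52, p = 0.009 on 2 df. Pairwise, with pooled variance:
- RCP v control: 0.10²/(0.25 × 0.75 × 0.02) = 2.67, p = 0.10
- RCP v BUP: 0.10²/(0.35 × 0.65 × 0.02) = 2.20, p = 0.14
- BUP v control: 0.20²/(0.30 × 0.70 × 0.02) = 9.52, p = 0.002

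The 2-df result is clearly significant and neither RCP contrast is. Item 12 does not say what would be concluded.

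**Effect of adding the missing step.** With 100 per cohort and RCP equal to control, requiring both the 2-df test and an unadjusted RCP-versus-control test to be significant gives (simulated):

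| RCP/BUP/control | 2-df alone | 2-df and RCP v control |
|---|---|---|
| 22.5/45/22.5% | 0.953 | 0.050 |
| 15/30/15% | 0.774 | 0.049 |
| 35/45/35% | 0.305 | 0.040 |
| 20/10/20% | 0.504 | 0.048 |
| 10/5/10% | 0.235 | 0.043 |

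**Several results.** Two outcomes at two time points give four tests. If any one significant result counted, the unadjusted error would be up to 1 − 0.95⁴ = 18.5% under independence.

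**The case against.** Several things can fairly be said for the plan.

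- **The test does bear on RCP.** A reader might infer that it can be significant solely because BUP and the historical control differ, leaving RCP out of it. That cannot be: if those two differ, RCP cannot equal both. In every scenario above where RCP equals control, RCP truly differs from BUP, a comparator the protocol names. What stands is that rejection does not locate the difference, give its direction or show benefit over control.
- **The rejection rates are not error rates.** A reader might take 79-97% as a false-positive rate for RCP. It is the chance of detecting a real cohort difference. A sensible follow-up test would hold false RCP-versus-control claims to 4-5%.
- **The comparators are named and the table would show each proportion,** so direction would be visible. True, but neither comparator is primary and no test is attached to either comparison.
- **The chi-square sentence follows the one on baseline characteristics** and might be meant only for those. The table note makes the wider reading more likely. On the narrow reading the primary outcomes would have no stated test, which is a larger gap.
- **Multiplicity is a separate matter.** A reader might infer an 18.5% error rate for this trial. The documents state no any-of-four rule, and the hypothesis joins its two parts with *and*. The rule is simply missing.
- **The illustrative rates are assumed.** The 2:1 ratio concerns engagement against a brief interview or referral. The documents do not establish it for printed resources, for the engagement-or-remission composite, or at 180 days.

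**Conclusion.** The point holds and should be fixed. The only stated test is non-directional over three cohorts, while the hypothesis is directional and about one. A significant result would show that RCP differs from BUP, from the historical control, or from both. It would not by itself support the claim that RCP reduces overdose or increases remission.

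The structural conclusion is firm because it rests on the text alone. The size rests on assumed rates and cohort sizes. With no RCP benefit over control, the test rejects in about 79-97% (100 per cohort) or 33-57% (33 each) for engagement if BUP doubles it, and about 24-49% (100 per cohort) for overdose if BUP halves it. For a composite at 35/45/35% it rejects in about 30% at 100 per cohort.

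**What to change.** In item 12:

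1. For each primary outcome, make the primary analysis a prespecified two-sided 1-df comparison of RCP with one named comparator, with a risk difference and 95% CI. The investigators choose from the two comparators already named, after confirming that the outcome exists for that comparator at that time point. The documents do not show whether the historical source has EPIC-identified repeat overdose or the 180-day composite.
2. Report the other RCP contrast in the same form as supportive.
3. Keep the 2-df test as a gate if wanted. With three groups, unadjusted pairwise tests after it control error within one outcome and time point. If only one contrast is tested, no gate is needed.
4. Name the primary time point and say whether both outcomes must succeed. If any one of the four results would count, use Holm or a similar procedure.
5. State that the cohorts are not randomised. Under item 7, criterion 16, RCP participants must have refused BUP where it was offered, so a significant contrast shows a cohort difference and not a proven intervention effect.

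**Cost.** A few sentences, and no data beyond the three-row table. The 80% power is not shown for any contrast and must be restated for the chosen one. At assumed rates, a 1-df test at 5% needs per group 69 (22.5 v 45%), 121 (15 v 30%), 199 (20 v 10%) or 435 (10 v 5%). Requiring both outcomes avoids an alpha split between them, but at 100 per cohort joint power for 22.5 v 45% and 20 v 10% is about 0.926 × 0.508 = 0.47 if independent. Keeping the gate lowers simulated RCP-versus-control power, when RCP equals BUP, from 0.93 to 0.91 (22.5 v 45%) or from 0.52 to 0.45 (20 v 10%).
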